4.1.2 Exclusion Criteria

Patients who meet any of the following criteria will be excluded from study entry:

- Stage IV (metastatic) breast cancer
- Inflammatory breast cancer (cT4d)
- Bilateral invasive breast cancer
- History of invasive breast cancer
- History of ductal carcinoma in situ or lobular carcinoma in situ if they have received any systemic therapy for treatment or radiation therapy to the ipsilateral breast
 - Patients treated with surgery alone may be eligible.
- History of other malignancy within 5 years prior to screening, except for appropriately treated carcinoma in situ of the cervix, non-melanoma skin carcinoma, or Stage I uterine cancer
- Previous systemic or local treatment for the primary breast cancer currently under investigation (including excisional biopsy or any other surgery of the primary tumor and/or axillary lymph nodes, radiotherapy, cytotoxic, and endocrine treatments)
- History of any prior treatment with AIs, tamoxifen, SERDs, or CDK4/6 inhibitors
- Major surgery within 4 weeks prior to randomization

- Known clinically significant history of liver disease consistent with Child-Pugh Class B or C, including hepatitis (e.g., hepatitis B virus [HBV] or hepatitis C virus [HCV]), current alcohol abuse, cirrhosis, or positive test for viral hepatitis as defined below:

Active infection is defined as requiring treatment with antiviral therapy or presence of positive test results for hepatitis B (hepatitis B surface antigen [HBsAg] and/or total hepatitis B core antibody [HBcAb]) or HCV antibody. Unless required by local regulations, patients are not required to have HIV, HBV, or HCV assessments at screening if these assessments have not been previously performed.

Patients who test positive for HBcAb are eligible only if test results are also positive for hepatitis B surface antibody and polymerase chain reaction is negative for HBV DNA.

Patients who are positive for HCV serology are only eligible if testing for HCV RNA is negative.

- Other severe acute or chronic medical or psychiatric condition or laboratory abnormality that may increase the risk associated with study participation or investigational product administration or may interfere with the interpretation of study results and, in the judgment of the investigator, would make the patient inappropriate for entry into this study
- History of allergy to anastrozole, or palbociclib or any of its excipients
- Known issues with swallowing oral medication
- History of documented hemorrhagic diathesis, coagulopathy, or thromboembolism
- Active cardiac disease or history of cardiac dysfunction including any of the following:
 - History or presence of symptomatic bradycardia or resting heart rate < 50 bpm at screening

Patients on stable dose of a β -blocker or calcium channel antagonist for pre-existing baseline conditions (e.g., hypertension) may be permitted if resting heart is ≥ 50 bpm.
 - History of angina pectoris, symptomatic pericarditis, myocardial infarction, or any cardiac arrhythmias (e.g., ventricular, supraventricular, nodal arrhythmias, or conduction abnormality) within 12 months prior to study entry
 - History of documented congestive heart failure (New York Heart Association Class II–IV) or cardiomyopathy
 - Left ventricular ejection fraction $< 50\%$ as determined by multiple-gated acquisition scan or echocardiogram
 - QT interval corrected through use of Fridericia's formula (QTcF) > 470 ms based on mean value of triplicate ECGs, history of long or short QT syndrome, Brugada syndrome or known history of corrected QT interval prolongation, or torsades de pointes

- History or presence of an abnormal ECG that is clinically significant in the investigator's opinion, including complete left bundle branch block, second- or third-degree heart block, sick sinus syndrome, or evidence of prior myocardial infarction
- History of ventricular dysrhythmias or risk factors for ventricular dysrhythmias such as structural heart disease (e.g., severe left ventricular systolic dysfunction, left ventricular hypertrophy), coronary heart disease (symptomatic or with ischemia demonstrated by diagnostic testing), clinically significant electrolyte abnormalities (e.g., hypokalemia, hypomagnesemia, hypocalcemia), or family history of long QT syndrome
- Current treatment with medications that are well known to prolong the QT interval (see Section 4.4.2.2)
- Active inflammatory bowel disease or chronic diarrhea, short bowel syndrome, or major upper gastrointestinal (GI) surgery including gastric resection
- Treatment with strong CYP3A4 inhibitors or inducers within 14 days or 5 drug elimination half-lives (whichever is longer) prior to randomization
- Known HIV infection
- Serious infection requiring oral or IV antibiotics, or other clinically significant infection within 14 days prior to screening
 - Patients who fully recovered from serious and clinically significant infections within 14 days prior to screening are eligible.
- Any serious medical condition or abnormality in clinical laboratory tests that, in the investigator's judgment, precludes the patient's safe participation in and completion of the study
- Assessed by the investigator to be unable or unwilling to comply with the requirements of the protocol

4.2 METHOD OF TREATMENT ASSIGNMENT

This is a randomized, open-label study. After initial written informed consent has been obtained, all screening procedures and assessments have been completed, and eligibility has been established for a patient, the study site will obtain the patient's identification number and treatment assignment from an interactive voice or web-based response system (IxRS).

Patients will be randomly assigned to one of two treatment arms: experimental arm or control arm. Randomization will occur in a 1:1 ratio through use of a permuted-block randomization method to ensure a balanced assignment to each treatment arm. Randomization will be stratified according to the following criteria:

- cT status: cT1c–cT2 versus cT3–cT4a–c
- Ki67 score: <20% versus ≥20%
- PgR status: positive versus negative

4.3 STUDY TREATMENT AND OTHER TREATMENTS RELEVANT TO THE STUDY DESIGN

The investigational medicinal products (IMPs) for this study are GDC-9545, anastrozole, and palbociclib.

4.3.1 Study Treatment Formulation and Packaging

4.3.1.1 GDC-9545

GDC-9545 will be supplied by the Sponsor as 30-mg capsules packaged in high-density polyethylene bottles with a plastic child-resistant cap with induction seal and desiccant. For information on the GDC-9545 formulation, see the pharmacy manual and the GDC-9545 Investigator's Brochure.

4.3.1.2 Anastrozole

Anastrozole will be supplied by the Sponsor as 1-mg film-coated tablets. For information on the anastrozole formulation, see the local prescribing information for anastrozole.

4.3.1.3 Palbociclib

Palbociclib will be supplied by the Sponsor as 75-, 100-, and 125-mg hard gelatin capsules. During the course of the study, the formulation may switch to 75, 100, and 125-mg tablets. For additional information on the palbociclib formulation and packaging, see the local prescribing information for palbociclib.

4.3.2 Study Treatment Dosage, Administration, and Compliance

The treatment regimens are summarized in Section 3.1 and outlined in [Figure 1](#) and [Figure 2](#).

[figure not shown]
Refer to the pharmacy manual for detailed instructions on drug preparation, storage, and administration.

To assess patient compliance with self-administration of study medication (GDC-9545, anastrozole, and palbociclib), site study staff will provide patients with detailed instructions and training for the handling and administration of study drugs. Patients will receive and should be instructed to complete a medication diary. Patients will be instructed to bring all unused study medication and their medication diaries to the clinic at specified study visits (see schedule of activities [Appendix 1](#)). Compliance will be assessed by investigator site team staff (e.g., by counting returned tablets/ capsules, clinic visit patient interview notes, and reviewing patient diaries).

Details on treatment administration should be noted on the Study Drug Administration electronic Case Report Form (eCRF). Cases of overdose, medication error, drug abuse, or drug misuse, along with any associated adverse events, should be reported as described in Section [5.3.5.11](#).

Guidelines for dosage modification and treatment interruption, or discontinuation for patients who experience adverse events are provided in Section [5.1.4](#).

Figure 2 Study Treatment Regimens

C = cycle; D = day.

4.3.2.1 GDC-9545, Palbociclib, and Anastrozole

GDC-9545, anastrozole, and palbociclib should be taken orally with food at approximately the same time each day as per study treatment regimen. If palbociclib switches to tablet formation (see Section 4.3.1.3), study treatments may be taken with or without food. The capsule or tablet should be swallowed whole and should not be chewed, crushed, or opened.

During the window-of-opportunity phase, GDC-9545 and anastrozole can be taken with or without food at approximately the same time each day. During the window-of-opportunity phase, starting on Cycle 0 Day 1, GDC-9545 30 mg PO QD or anastrozole 1 mg PO QD will be administered as a single agent for 2 weeks.

During the neoadjuvant treatment phase, GDC-9545 30 mg PO QD or anastrozole 1 mg PO QD will be administered on Days 1–28 of each 28-day cycle in combination with palbociclib 125 mg PO QD on Days 1–21 of each 28-day cycle for four cycles. Starting with Day 1 of Cycle 0 and on Day 1 of each 28-day cycle thereafter, study treatment will be administered in the clinic after the study assessments, as indicated in the schedule of activities (see Appendix 1 and Appendix 2). All other doses will be taken at home on all non-clinic visit days. If a GDC-9545 dose is missed, the dose should be made up unless the next dose is due within 6 hours.

4.3.2.2 Compliance

At the beginning of study participation by a patient, site study staff will provide the patient with detailed instructions and training for the handling and administration of study treatment. Patients will receive and should be instructed to complete a medication diary.

At each clinic visit, the medication diary as well as unused tablets or capsules and all containers or packaging (used or unused) of study treatment should be collected and reviewed for drug accountability.

Treatment compliance will be defined as the number of capsules or tablets taken divided by the expected number of capsules or tablets and reported as a percentage. In case of dose reductions, the expected number of capsules or tablets should reflect the new dose level. Capsules or tablets that are not returned will be considered to have been taken, unless otherwise specified in the patient's diary and/or eCRF. Note that dosing eCRFs should be completed using the following prioritization: 1) site pharmacy drug accountability logs (IMP disbursed minus IMP returned), 2) clinic visit patient interview notes, and 3) patient daily dosing diary.

4.3.3 Investigational Medicinal Product Accountability

All IMPs required for completion of this study will be provided by the Sponsor. The study site (i.e., investigator or other authorized personnel [e.g., pharmacist]) is responsible for maintaining records of IMP delivery to the site, IMP inventory at the site, IMP use by each patient, and disposition or return of unused IMP, thus enabling reconciliation of all IMP received, and for ensuring that patients are provided with doses specified by the protocol.

The study site should follow all instructions included with each shipment of IMP. The study site will acknowledge receipt of IMPs supplied by the Sponsor, using the IxRS to confirm the shipment condition and content. Any damaged shipments will be replaced. The investigator or designee must confirm that appropriate temperature conditions have been maintained during transit for all IMPs received and that any discrepancies have been reported and resolved before use of the IMPs. All IMPs must be stored in a secure, environmentally controlled, and monitored (manual or automated) area in accordance with the labeled storage conditions, with access limited to the investigator and authorized staff.

Only patients enrolled in the study may receive IMPs, and only authorized staff may supply or administer IMPs.

IMPs will either be disposed of at the study site according to the study site's institutional standard operating procedure or be returned to the Sponsor with the appropriate documentation. The site's method of destroying Sponsor-supplied IMPs must be agreed to by the Sponsor. The site must obtain written authorization from the Sponsor before any Sponsor-supplied IMP is destroyed, and IMP destruction must be documented on the appropriate form.

Accurate records of all IMPs received at, dispensed from, returned to, and disposed of by the study site should be recorded on the drug accountability log.

Refer to the pharmacy manual and/or the GDC-9545 Investigator's Brochure and the anastrozole and palbociclib local prescribing information for information on IMP handling, including preparation and storage, and accountability.

4.3.4 Continued Access to GDC-9545

Currently, the Sponsor does not have any plans to provide Roche IMP (GDC-9545) or any other study treatments to patients who have completed the study. The Sponsor may evaluate whether to continue providing GDC-9545 in accordance with the Roche Global Policy on Continued Access to Investigational Medicinal Product, available at the following website:

http://www.roche.com/policy_continued_access_to_investigational_medicines.pdf

4.4 CONCOMITANT THERAPY, PROHIBITED FOOD, AND ADDITIONAL RESTRICTIONS

Concomitant therapy consists of any medication (e.g., prescription drugs, over-the-counter drugs, vaccines, herbal or homeopathic remedies, nutritional supplements) used by a patient in addition to protocol-mandated treatment from 7 days prior to initiation of study drug to treatment discontinuation or end of study visit. All such medications should be reported to the investigator and recorded on the Concomitant Medications eCRF.

GDC-9545 is primarily glucuronidated via UGT1A4. It is unlikely that any clinically relevant drug-drug interaction (DDI) will occur with GDC-9545 both as a perpetrator and as a victim. Palbociclib is primarily metabolized by CYP3A and sulfotransferase enzyme SULT2A1. In vivo, palbociclib is a time-dependent inhibitor of CYP3A.

4.4.1 Permitted Therapy

Patients are permitted to use the following therapies during the study:

- Symptomatic anti-emetics and anti-diarrheal therapy may be administered at the investigator's discretion.
- Bone-sparing agents (e.g., bisphosphonates, denosumab for the treatment of osteoporosis/osteopenia) are allowed in the study provided patients are on stable doses for at least 4 weeks prior to randomization.
- Patients can be treated per standard of care except for use of any prohibited therapies.

All concomitant medication and/or therapies should be documented in the patient's eCRF.

4.4.2 Cautionary Therapy

4.4.2.1 CYP3A4 Substrate with a Narrow Therapeutic Index

Co-administration of midazolam (sensitive CYP3A4 substrate) with multiple doses of palbociclib increased the midazolam plasma exposure by 61% in healthy subjects

compared with the administration of midazolam alone. Therefore, the dose of a sensitive CYP3A4 substrate with a narrow therapeutic index (e.g., alfentanil, cyclosporine, dihydroergotamine, ergotamine, everolimus, fentanyl, pimozone, quinidine, sirolimus, and tacrolimus) may need to be reduced, as palbociclib may increase its exposure (Ibrance® U.S. Package Insert).

The above list of CYP3A4 sensitive substrates with a narrow therapeutic index is not necessarily comprehensive. Thus, the investigator should consult the prescribing information for any concomitant medication as well as the internet reference provided below when determining whether a medication is a sensitive CYP3A4 substrate with a narrow therapeutic index and can be safely administered with palbociclib. Palbociclib local prescribing information should also be consulted for information on prohibited therapies and recommended dose adjustments for concomitant medications. In addition, the investigator should contact the Medical Monitor if questions arise regarding medications not listed above.

<http://www.fda.gov/downloads/Drugs/GuidanceComplianceRegulatoryInformation/Guidances/UCM292362.pdf>

4.4.2.2 Medications Associated with QT Interval Prolongation

Any concomitant medications known to affect QT interval duration, including, but not limited to, the following drugs and drug classes should be used with caution and an alternative therapy should be used when possible: fluoroquinolones, antifungals (i.e., ketoconazole, itraconazole, and fluconazole), antimalarials, amiodarone, cisapride, clarithromycin, erythromycin, methadone, amitriptyline, maprotiline, clomipramine, citalopram, escitalopram, venlafaxine, quinidine, and Class 1 and 3 antiarrhythmics.

Investigators should use medical judgement and exercise caution when considering the co-administration of drugs known to cause decrease in heart rate in patients already receiving treatment with GDC-9545, and an alternative therapy should be used when possible.

Medications Associated with Bradycardia

Investigators should use medical judgment and exercise caution when considering initiation of concomitant medication known to cause decreases in heart rate including, but not limited to, β -blockers and calcium channel antagonists. An alternative therapy should be used when possible. Patients on a stable dose of a β -blocker or calcium channel antagonist for preexisting baseline conditions (e.g., hypertension) should be monitored closely in case dose modification is warranted.

4.4.2.3 Herbal Therapies

Concomitant use of herbal therapies, especially St. John's wort (strong CYP3A inducer), in combination with palbociclib is not recommended because their pharmacokinetics, safety profiles, and potential DDIs are generally unknown. However, other herbal

therapies (excluding St. John's wort) not intended for the treatment of cancer may be used during the study at the discretion of the investigator and must be reported as concomitant therapy in the eCRF.

4.4.3 Prohibited Therapy

Use of the following concomitant therapies is prohibited during study treatment as described below:

- Strong CYP3A4 inhibitors, including, but not limited to, the following: atazanavir, ritonavir, lopinavir, telaprevir, telithromycin, indinavir, nelfinavir, saquinavir, clarithromycin, troleandomycin, itraconazole, ketoconazole, voriconazole, posaconazole, conivaptan, diltiazem, nefazodone, and mibefradil

If co-administration of palbociclib with a strong CYP3A4 inhibitor cannot be avoided, reduce the dose of palbociclib as per palbociclib local prescribing information.

- Strong CYP3A4 inducers, including, but not limited to, the following: rifampin, carbamazepine, phenytoin, enzalutamide, oxcarbazepine, phenobarbital, nevirapine, hyperforin (St. John's Wort), and cyproterone

The above lists of CYP3A4 concomitant medications are not necessarily comprehensive. Thus, the investigator should consult the prescribing information for any concomitant medication as well as the internet reference provided below when determining whether a certain medication strongly inhibits or induces CYP3A4. Palbociclib and anastrozole local prescribing information should also be consulted for information on prohibited therapies and recommended dose adjustments for concomitant medications. In addition, the investigator should contact the Medical Monitor if questions arise regarding medications not listed above.

<http://www.fda.gov/downloads/Drugs/GuidanceComplianceRegulatoryInformation/Guidances/UCM292362.pdf>

- Investigational therapy (other than protocol-mandated study treatment) is prohibited during study treatment.
- Any concomitant therapy intended for the treatment of cancer (including, but not limited to, chemotherapy, hormonal therapy, immunotherapy, biologic therapy, or radiotherapy) is prohibited until after the end of study visit. Adjuvant endocrine therapy may be used after surgery at the investigator's discretion. Adjuvant chemotherapy, if indicated, may be initiated after the completion of the mandatory end-of-study visit.
- Hormone replacement therapy, topical estrogens (including any intra-vaginal preparations), megestrol acetate, oral contraception, hormone-eluting intrauterine devices, Gonadotropin-releasing hormone (GnRH) agonists and selective ER modulators (e.g., raloxifene) are prohibited until after the end of study visit.

- Primary prophylactic use of hematopoietic growth factors (e.g., erythropoietins, granulocyte colony-stimulating factor, and granulocyte-macrophage colony-stimulating factor) is not permitted; however, they may be used to treat treatment-emergent neutropenia or anemia as indicated by the current ASCO guidelines or as secondary prophylaxis if dose reduction or delay is not considered a reasonable alternative and with approval of the Medical Monitor.

Enrolled patients who subsequently require the use of any prohibited therapies must be discontinued from study treatment as outlined in Section 4.6.1.

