4.6 TREATMENT, PATIENT, STUDY, AND SITE DISCONTINUATION

4.6.1 Study Treatment Discontinuation

Patients must permanently discontinue study treatment if they experience any of the following:

- Any medical condition that the investigator or Sponsor determines may jeopardize the patient's safety if he or she continues to receive study treatment
- Investigator or Sponsor determination that treatment discontinuation is in the best interest of the patient
- Intolerable toxicity related to study treatment determined by the investigator to be unacceptable given the potential for treatment benefit and the severity of the event
- Disease progression per investigator's assessment
- Non-compliance with protocol specified drug administration and follow-up tests
- Concomitant use of any other (non-protocol) systemic anti-cancer therapy
- Pregnancy

The primary reason for study treatment discontinuation should be documented on the appropriate eCRF.

Patients will return to the clinic for an end of study visit 28 (\pm 3) days after the final dose of study drug (see [Appendix 1](#) for additional details).

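### For a patient who cannot avoid a strong CYP3A4 inhibitor, Section 4.4.3 gives two opposite instructions: change the palbociclib dose, or discontinue study treatment

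*Combined protocol and SAP*

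**What the plan says.** Section 4.4.3 opens its list with "Use of the following concomitant therapies is prohibited during study treatment as described below". Strong CYP3A4 inhibitors are the first entry, with 18 agents named. Directly under that entry stands: "If co-administration of palbociclib with a strong CYP3A4 inhibitor cannot be avoided, reduce the dose of palbociclib as per palbociclib local prescribing information". Strong inducers follow without a dose sentence of their own; there is only a general referral to the local prescribing information. The section ends: "Enrolled patients who subsequently require the use of any prohibited therapies must be discontinued from study treatment as outlined in Section 4.6.1".

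Section 4.6.1 lists the reasons for permanent discontinuation. Its only trigger based on a concomitant drug is "Concomitant use of any other (non-protocol) systemic anti-cancer therapy".

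Section 2 defines study treatment as the assigned combination, so it is not limited to palbociclib. Section 5.1.4.2 allows the endocrine partner to go on to Cycle 4 after palbociclib has been permanently stopped.

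Two cautionary sections also touch agents on the prohibited lists. Section 4.4.2.2 says of drugs that affect the QT interval that they "should be used with caution and an alternative therapy should be used when possible: fluoroquinolones, antifungals (i.e., ketoconazole, itraconazole, and fluconazole"; clarithromycin comes later in the same list. Section 4.4.2.3 says "Concomitant use of herbal therapies, especially St. John's wort (strong CYP3A inducer), in combination with palbociclib is not recommended".

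**The concern.** The dose sentence and the closing sentence of Section 4.4.3 describe the same patient: one who needs a strong inhibitor and has no alternative. One sentence keeps her on palbociclib at a changed dose. The other takes her off study treatment, and under the Section 2 definition that includes GDC-9545 or anastrozole.

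The first stake is patient safety and consistent conduct across about 90 sites. The second is who completes the 16 weeks of combination treatment. Section 6.2 calls for a summary of major protocol deviations, yet on this point there is no single rule against which to judge a deviation.

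**Working it through.** The plan attaches no figure to this rule, so the check sets the texts side by side.

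**1. Same patient, neoadjuvant phase, strong inhibitor unavoidable**

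| Source | Consequence |
|---|---|
| 4.4.3, sentence under the inhibitor entry | Stays on palbociclib at a changed dose |
| 4.4.3, closing sentence | Discontinued from study treatment |
| 4.6.1, the section cited | Not listed as a reason |
| 5.1.4.2, if only palbociclib is stopped | Endocrine partner may continue |

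The first two rows cannot both be followed. The third does not decide between them. The fourth leaves open whether discontinuation means palbociclib or everything.

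**2. Which agents.** The dose sentence covers inhibitors only, so the direct contradiction is confined to that class. For inducers the text gives prohibition and discontinuation, plus the general label referral.

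**3. Which phase.** Palbociclib starts only after the Week 2 biopsy (Appendix 2, note e). In the 14-day window there is no palbociclib dose to change, so there the closing sentence has no competing instruction. Section 4.1.2 excludes recent users of strong inhibitors or inducers, so the question arises for needs that appear after enrolment.

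**4. Reach into the endpoints**

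- *Objective response (Section 6.4.2).* Patients with no post-baseline tumour assessment count as non-responders. The one mandatory post-baseline ultrasound comes after the last combination dose, specified as after Cycle 4 Day 21 and before surgery (Section 4.5.7). A patient taken off early can miss it, or be assessed after less treatment.
- *Week 2 Ki67 (Section 6.4.1).* A patient is lost only if discontinued before the Day 15 biopsy. The plan allows for 6% missing: 0.06 × 215 = 12.9, in line with 215 − 202 = 13. Nothing in the documents suggests that this rule would use up that allowance.

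**5. Overlap with the cautionary sections.** Comparing the named drugs in 4.4.2.2 with the 18 prohibited inhibitors gives three in common: ketoconazole, itraconazole and clarithromycin. One named inducer, St. John's wort, appears in both 4.4.2.3 and 4.4.3.

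**The case against.** The best defence is that Section 4.4.3 states a rule with an exception. The dose sentence sits under the inhibitor entry and qualifies it, and the section uses that form elsewhere: growth factors are barred as primary prophylaxis but allowed to treat neutropenia or anaemia, and anti-cancer therapy is barred but adjuvant endocrine therapy is allowed after surgery. On that reading the closing sentence covers only use outside the stated exceptions. This is a reasonable reading, and it may be what was meant. But the closing sentence is unqualified, comes last, and is aimed at patients who require the drug, which is nearly the same condition as being unable to avoid it. If the exception governs, the closing sentence has almost nothing left to do for strong inhibitors once palbociclib has started. The text does not say which prevails.

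It can also be said that the Section 4.6.1 list is not declared exhaustive, that its best-interest item could cover the case, and that the reference may be only to its procedure. That is fair, and silence there does not contradict Section 4.4.3. It does mean that the cross-reference gives a site no help. As for Section 5.1.4.2, it is written around toxicity, so its palbociclib provision may not have been meant for a prohibited drug; again, the text does not say.

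A reader might go further and infer that caution, dose change, prohibition and discontinuation all collide for inhibitors and inducers alike. The documents do not support that:

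- Inducers have no dose sentence.
- The Section 4.4.2.2 caution concerns QT risk and can apply alongside the prohibition.
- Section 4.4.2.3 leaves herbal products to the investigator's discretion but expressly excludes St. John's wort.

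What remains on those two sections is a missing cross-reference.

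**Conclusion.** The contradiction stands for strong CYP3A4 inhibitors: two sentences of Section 4.4.3 lead to opposite outcomes for one patient, and the related sections do not resolve it. Sites can diverge; the documents do not show that they will.

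The size cannot be stated. A reader might assume that 2% to 5% of patients need such a drug (215 × 0.02 = 4.3; 215 × 0.05 = 10.8) and conclude that about 4 to 11 are handled inconsistently. No source in the documents supports that rate, and the step also assumes that every such patient is handled inconsistently.

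The endpoint consequences are modest. Early discontinuation does not by itself make a patient a non-responder. Both arms receive palbociclib, and nothing points to a difference between them. The primary endpoint is touched only through discontinuation before Day 15, and the sample size is unaffected. The point should be corrected because it concerns when treatment is stopped and the correction is cheap, not because it threatens the main comparison.

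**What to change.** The sponsor's clinical team should reconcile Sections 4.4.3, 4.6.1 and 5.1.4.2 so that:

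- an unavoidable strong CYP3A4 inhibitor has one stated consequence, with any exception written into the closing sentence of Section 4.4.3 or the competing sentence removed;
- the text says whether that consequence applies to palbociclib alone or to all study treatment, and whether it differs between the window and neoadjuvant phases;
- Section 4.6.1 either lists the trigger or is cited for procedure only.

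Which rule applies is a clinical decision and is not proposed here.

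As secondary tidying, add cross-references from Section 4.4.2.2 (ketoconazole, itraconazole, clarithromycin) and Section 4.4.2.3 (St. John's wort) to the Section 4.4.3 prohibition, so that neither can be read as permission.

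The cost is amendment wording and a note to sites. No analysis or sample size changes.
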